6.1.1. Sensitivity/Supplementary Analysis

If the data permits, palatability of sisunatovir may be analyzed using a mixed effects model. Data from multiple time points will be combined to be treated as the response. Treatment, sequence, timepoint, and period will be fixed effects; and participant within sequence will be a random effect. Estimates and corresponding 90% CIs will be obtained from the model.

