6.1.1. Administration

All formulations will be offered to all participants for tasting in a blinded fashion. Participants will taste approximately [] mL of a [] mg/mL suspension of sisunatovir, given in a randomized order. Participants will swirl the sample in the mouth for approximately 10 seconds, and then spit it out. Participants will assess various aspects of the taste using the questionnaire in [Appendix 9: Oral Solution or Suspension Palatability Questionnaire](#) at approximately 1 minute, 5 minutes, 10 minutes, and 20 minutes after dosing. There will be at least 60 minutes between tasting of each study intervention, and participants should rinse their mouth with ambient temperature water after completion of the questionnaire and prior to the next tasting. Drinking of water to cleanse palate is allowed except within 30 minutes to the start of the subsequent assessment, and meals can be taken and completed at least 60 minutes before the start of an assessment (see Section [5.3.2](#)).

Administration of study intervention(s) at the site will be performed by an appropriately qualified and trained member of the study staff as allowed by local, state, and institutional guidance.

Following administration of study intervention(s) at the site, participants will be observed for 20 minutes by an appropriately qualified and trained member of the study staff. Appropriate medication and other supportive measures for management of a medical emergency will be available in accordance with local guidelines and institutional guidelines.

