3. ENDPOINTS AND BASELINE VARIABLES: DEFINITIONS AND CONVENTIONS

3.1. Primary Endpoint(s)

3.1.1. Palatability Assessment Questionnaire Scoring Metrics: mouth feel, bitterness, sweetness, sourness, saltiness, tongue/mouth burn, overall liking

Participants will swirl the sample in the mouth for approximately 10 seconds, and then spit it out. Participants will assess various aspects of the taste, including mouth feel, bitterness, sweetness, sourness, saltiness, tongue/mouth burn, and overall liking using the Oral Solution or Suspension Palatability Questionnaire (Appendix 2).

Palatability assessments will be carried at approximately 1 minute, 5 minutes, 10 minutes, and 20 minutes after dosing.

The data collected for palatability assessment using the sponsor-provided palatability questionnaire will be numerically derived by measuring length (using a scale with gradations of at least 0.1 cm) of the 'x' marked by the participant relative to the 'good trait'. For palatability assessment, the data used in the analysis will be transcribed and rescaled to a score from 0 to 100 from the raw measurements on the questionnaire.

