5. GENERAL METHODOLOGY AND CONVENTIONS

5.1. Hypotheses and Decision Rules

No statistical hypothesis will be tested in this study.

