5.3. Methods to Manage Missing Data

For the analysis of safety endpoints, the sponsor data standard rules for imputation will be applied.

6. ANALYSES AND SUMMARIES.

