6.1. Primary Endpoint(s)

The sensory attributes (mouth feel, bitterness, sweetness, sourness, saltiness, tongue/mouth burn, overall liking) from the palatability questionnaires ([Appendix 2](#)) will be listed and descriptively summarized by session, time point, and treatment, if appropriate. Summary statistics (mean and 90% CI) will be calculated for the various questions. Radar plots for each of 4 time points, summarizing all attributes will be generated. Boxplots of each attribute will be plotted against the time points. Any additional feedback data as collected by the palatability questionnaire will be listed.

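### The optional mixed model in SAP 6.1.1 stacks four scores per tasting with no tasting-level term, so its 90% CIs for formulation differences are unreliable if only the listed terms are fitted

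*SAP*

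**What the plan says.** - **Status.** SAP 6.1.1 makes the model supplementary and optional: "If the data permits, palatability of sisunatovir may be analyzed using a mixed effects model".
- **Response and terms.** "Data from multiple time points will be combined to be treated as the response". The fixed effects are treatment, sequence, timepoint and period, and "participant within sequence will be a random effect". Estimates with 90% CIs are then taken from the model. Because timepoint is itself a model term, the four scores must enter as separate rows, not as an average.
- **Scores per tasting.** SAP 3.1.1: "Palatability assessments will be carried at approximately 1 minute, 5 minutes, 10 minutes, and 20 minutes after dosing". Protocol 6.1.1 has the sample swirled once and spat out, and adds that "participants should rinse their mouth with ambient temperature water after completion of the questionnaire and prior to the next tasting". The four scores are therefore repeated readings of one administration.
- **What is not specified.** SAP 6.1.1 names no participant-by-period effect, residual covariance or denominator df method. SAP 5.2 to 5.3 and Protocol section 9 supply none. It also does not say whether the estimates are formulation differences or adjusted means. Its parent section, SAP 6.1, says "Summary statistics (mean and 90% CI) will be calculated for the various questions", while Protocol 4.2 gives comparison within participants as the reason for the crossover.
- **Inference.** SAP 5.1: "No statistical hypothesis will be tested in this study".

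**The concern.** The unit that receives a formulation is the tasting (one participant in one period). A random participant effect removes a person's general scoring level. It does not remove what the four scores of one mouthful share beyond that level. If that shared part is not modelled, four readings of one tasting count as four independent replicates of the formulation.

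The text also permits two different models. One analyst could fit only the listed terms. Another could add a repeated-measures covariance without contradicting the SAP. They would report different intervals for the same formulation difference. With no hypothesis tests, a reader would judge those differences by interval width.

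**Working it through.** **1. The plan's own precision figure.** Protocol 9.5 gives half-widths of a 90% CI for one mean score, n = 12, with 80% probability. The formula t(0.95, 11) × SD × √(χ²(0.80, 11)/11)/√12 equals 0.598 × SD. It gives 10.76, 15.55, 13.57, 14.59, 14.05 and 10.58, against the stated 10.8, 15.5, 13.6, 14.6, 14.0 and 10.6. The table reproduces. It concerns one mean over 12 participants, so stacking does not touch it.

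**2. Degrees of freedom.** The sample dosing scheme has 12 participants with 7 tastings each: 12 × 7 = 84 tastings and 84 × 4 = 336 scores per attribute. Parameters are 12 (participants, absorbing sequence) + 5 (treatment) + 7 (period) + 3 (timepoint) = 27.
- Listed terms only: 336 − 27 = 309 residual df.
- Tasting level (no timepoint term): 84 − 24 = 60 residual df.

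**3. Model SE against true SE.** Set the within-participant variance of one score to 1. Let r be the mean pairwise correlation among the four scores of a tasting beyond the participant effect.
- Expected residual mean square: [249(1 − r) + 60(1 + 3r)]/309 = 1 − 0.223r. Here 249 = 309 − 60 is the within-tasting df.
- True variance of a formulation difference is proportional to 1 + 3r.
- True SE / model SE = √[(1 + 3r)/(1 − 0.223r)].

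The documents give no correlation, so it is assumed in two forms: equal correlation (r = rho), and decay over time, where a gap of g minutes has correlation rho^(g/4) and rho is the 1-to-5-minute value. Coverage of the nominal 90% CI for B minus A is simulated (20,000 runs per cell).

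| rho | Equal: SE ratio | Equal: coverage | Decay: mean r | Decay: SE ratio | Decay: coverage |
|---|---|---|---|---|---|
| 0 | 1.00 | 90% | 0 | 1.00 | 90% |
| 0.1 | 1.15 | 85% | 0.028 | 1.04 | 88% |
| 0.25 | 1.36 | 77% | 0.085 | 1.13 | 86% |
| 0.5 | 1.68 | 67% | 0.236 | 1.34 | 78% |
| 0.9 | 2.15 | 55% | 0.769 | 2.00 | 59% |

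These runs fit participant as fixed, which gives the same contrasts when data are complete. REML fits with participant random (40% of variance between participants) gave 86%, 78%, 67% and 55% (equal) and 88%, 85%, 79% and 57% (decay) at rho 0.1, 0.25, 0.5 and 0.9. With participant-driven correlation only (rho 0, 20% to 80% between participants), coverage was 90% to 91%. For all 15 pairs the stacked variance factor is one quarter of the tasting-level factor: 0.0417 against 0.1667 for 9 pairs, and 0.0833 against 0.3333 for the 6 pairs of B, C or D with E or F.

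**4. Offsets.** Two omitted effects inflate the residual mean square without changing the true variance of a time-averaged difference:
- treatment-by-timepoint interaction with mean square φ² adds (336/309)φ² = 1.087φ²;
- participant-by-timepoint variance ψ adds (33 × 7/309)ψ = 0.748ψ, where 33 = 48 − 12 − 3.

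Model SE / true SE becomes √[(1 − 0.223r + 1.087φ² + 0.748ψ)/(1 + 3r)]. Coverage is approximately 2Φ(1.65 × that ratio) − 1.

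| Setting | No offset | φ = 0.5 SD | ψ = 0.5 | Both |
|---|---|---|---|---|
| Equal 0.1 | 85% | 89% | 91% | – |
| Decay 0.25 | 86% | 89% | 91% | 94% |
| Equal 0.25 | 77% | 83% | 85% | – |
| Equal 0.5 | 67% | 73% | 76% | 80% |

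Example, equal 0.5 with both: (0.8885 + 0.272 + 0.374)/2.5 = 0.614, square root 0.783, coverage 80%. An interaction of 0.75 SD at decay 0.25 gives 94%, which is too wide. Tasting-level intervals covered 89% to 91% in every scenario checked.

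**5. In points.** Take the Overall Liking SD of 22.7 (Protocol 9.5, from another study's Bitrex group, so an assumption), 40% of variance between participants, rho 0.5 and no offset. The within-participant SD is 22.7 × √0.6 = 17.6, so 0.5 SD is 8.8 points. Half-width for B minus A:
- listed terms: 1.650 × 17.6 × √(0.0417 × 0.8885) = 5.6;
- tasting level: 1.671 × 17.6 × √(0.1667 × 2.5/4) = 9.5;
- with decay (r = 0.236): 5.8 and 7.8.

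For the 6 different-day pairs the figures are 7.9 and 13.4 (decay 8.1 and 11.1).

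**6. Adjusted means.** At rho 0.5 and 40% between participants, true SE / model SE is 1.22 for B and 1.08 for A (equal), and 1.10 and 1.03 (decay). At 20% it is 1.39 and 1.14, and 1.19 and 1.06.

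**The case against.** The strongest case against has four parts.

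- **Direction.** A reader might infer that the intervals are bound to be too narrow, or that only a very large interaction could cancel the narrowing. The documents do not support either. Scores run from 1 to 20 minutes and the formulations differ in flavour and sweetener, so some treatment-by-timepoint interaction is plausible, as is variation between participants in how fast taste fades. At equal correlation 0.1 or decay 0.25, moderate amounts of either restore nominal coverage, and more makes the intervals too wide. This stands. It does not rescue the model, because two omissions cancel only by chance, and under-coverage remains at equal correlation 0.5.
- **Which estimate.** SAP 6.1 reports means, so adjusted means are a natural reading of SAP 6.1.1, and the error in them is smaller. This stands, and it is why the SAP should name the estimate.
- **The text is permissive.** A covariance structure could be added without contradicting the SAP. True, but nothing requires it, so the interval depends on who programs it.
- **Weight.** The model may not be run, and no hypothesis or decision rule rests on it. This stands and limits the point to minor. A reader should not extend it to the primary summaries, which are made by session, time point and treatment and do not stack the scores.

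**Conclusion.** The concern holds in limited form. Fitted with only its listed terms, the SAP 6.1.1 model takes its error for formulation differences from 309 df of mostly within-tasting variation instead of 60 df between tastings, so its 90% CIs are not reliable. Without offsets, coverage falls to between 85% and 55% over equal correlations of 0.1 to 0.9, and to between 88% and 59% with decay. With moderate unmodelled time effects it is about 89% to 91% at low to moderate correlation (equal 0.1 or decay 0.25), and about 73% to 80% at equal correlation 0.5.

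These sizes rest on assumed correlations, offsets and between-participant shares, on an SD borrowed from another study, and on the sample dosing scheme with complete data. What does not rest on them is that the error term is taken at the wrong level and that the SAP leaves the covariance and the reported estimate open. Severity: minor.

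**What to change.** In SAP 6.1.1:

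1. Add a participant-by-period (tasting) random effect, or a repeated-measures covariance over the four time points within each tasting, with tasting-level denominator df (for example Kenward-Roger).
2. State whether formulation differences, adjusted means or both are reported.

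Alternatives have limits. Fitting the crossover model to tasting means gives the same contrasts as the tasting random effect when all four scores are present and the tasting variance is not estimated at zero. It needs a rule for missing scores, because SAP 5.3 covers safety only: "For the analysis of safety endpoints, the sponsor data standard rules for imputation will be applied". Separate fits at each time point are valid but estimate four time-specific contrasts. A treatment-by-timepoint term alone is not a fix, because it only removes one of the offsets.

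The cost is one model term and a sentence of SAP text, with no new data. In many cases the intervals widen. In the Overall Liking example the half-width for B minus A rises from 5.6 to 9.5 points with equal correlation, or from 5.8 to 7.8 with decay.

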6.2. Secondary Endpoint(s)

The secondary endpoints are related to safety/tolerability and their analyses are described in [Section 6.5](#).

6.3. Subset Analyses

There are no planned subset analyses.

6.4. Baseline and Other Summaries and Analyses

6.4.1. Demographic Summaries

Demographic characteristics will be summarized for enrolled population in accordance with the sponsor reporting standards.

6.4.2. Study Conduct and Participant Disposition

Participants evaluation groups will show end of study participant disposition. Frequency counts will be supplied for participant discontinuation(s) by overall and treatment. Data will be reported in accordance with the sponsor reporting standards.

6.4.3. Study Treatment Exposure

Study treatment exposure will be listed.

6.4.4. Concomitant Medications and Nondrug Treatments

All concomitant medication(s) as well as non-drug treatment(s) will be reported in the listings according to current sponsor reporting standards.

6.5. Safety Summaries and Analyses

All safety analyses will be performed on the Safety analysis set.

Safety data will be presented in tabular and/or graphical format and summarized descriptively, where appropriate.

6.5.1. Adverse Events

Adverse events will be reported in accordance with the sponsor reporting standards.

Participant discontinuations due to adverse events will be detailed by treatment, where appropriate. Data will be reported in accordance with the sponsor reporting standards.

6.5.2. Clinical Laboratory Assessments

Laboratory data will be summarized by nominal timepoint in accordance with the sponsor reporting standards. Changes from baseline will be reported. Baseline is as defined in [Section 3.5.2](#).

6.5.3. Vital Signs

Vital signs data will be summarized by nominal timepoint in accordance with the sponsor reporting standards. Changes from baseline will be reported. Baseline is as defined as in [Section 3.5.3](#).

6.5.4. Electrocardiograms

ECG data will be summarized by nominal timepoint in accordance with the sponsor reporting standards. Baseline is as defined in [Section 3.5.4](#). Changes from baseline for the ECG parameters HR, QTcF, PR interval, and QRS complex will summarized using sponsor reporting standards. These correspond to the Pfizer Guidance¹ in [Section 8](#).

The frequency of uncorrected QT values above 500 ms will be tabulated.

The number (%) of participants with maximum postdose QTcF values and maximum increases from baseline in the following categories in [Table 2](#) will be tabulated.

Table 2. Categorical Classes for ECGs of Potential Clinical Concern

Degree of Prolongation	Mild (ms)	Moderate (ms)	Severe (ms)
Absolute value of QTcF	>450-480	>480-500	>500
Increase from baseline in QTcF		>30 and \leq 60	>60

Absolute values and changes from baseline in QT, heart rate, QTcF, PR and QRS will be listed using sponsor reporting standards.

Listings of participants with any single post-dose QTcF value >500 msec will also be produced.

7. INTERIM ANALYSES

No interim analysis will be conducted for this study.

Appendix 1. List of Abbreviations

Abbreviation	Term
AE	adverse event
CI	confidence interval
ECG	electrocardiogram
HR	heart rate
mg	milligram
mL	millilitre
N/A	not applicable
QTc	corrected QT
QTcF	corrected QT (Fridericia method)
SAP	statistical analysis plan
SD	standard deviation
SOP	standard operating procedure
TEAE	treatment-emergent adverse event

Appendix 2. Oral Solution or Suspension Palatability Questionnaire

1. Questionnaire should be administered to adult participants, preferably by a nurse.
2. Use colored copy of the Palatability Questionnaire.
3. Do not alter (reduce or enlarge) the original size of the Palatability Questionnaire.
4. Please collect the following background information:

Background Information

Study #/Study Site	
Period and Day	
Participant ID (Rand ID)	
Treatment	

Collect Date	
Collected By	
Entered in PIMS By	
Checked in PIMS By	
Questionnaire Fully Completed (circle one)	Yes/No

Please answer the following questions and provide a mark (X) on the color bar at approximately 1 (immediately), 5, 10 and 20 minutes after dosing. Please ensure participant has access to these descriptions when completing the questionnaire.

Q1: Mouth feel – Please tell us about the mouth feel (such as grittiness, stickiness, waxiness) of the product you tasted. Good represents normal mouth feel. Bad represents bad mouth feel.

Q2: Bitterness – Please tell us about the degree of bitterness of the product you tasted. Good represents not bitter at all. Bad represents extremely bitter.

Q3: Sweetness – Please tell us about the degree of sweet taste of the product you tasted. Good represents sweet. Bad represents not sweet at all.

Q4: Sourness – Please tell us about the degree of sour taste of the product you tasted. Good represents not sour at all. Bad represents extremely sour.

Q5: Saltiness – Please tell us about the degree of salty taste of the product you tasted. Good represents not salty at all. Bad represents extremely salty.

Q6: Tongue/mouth burn – Please tell us about the degree of tongue/mouth burn of the product you tasted. Good represents no burn at all. Bad represents extreme burn.

Q7: Overall liking – Please indicate how much you like or dislike the product you tasted. Good represents like. Bad represents dislike.

Details to assess questionnaire described below:

After the participants places the mark (X) on the color bar, the main Clinical Coordinator of the study and his back up or designee will proceed follows:

- ① Measuring the total length of the bar on the printed questionnaire:

- Place the 30 cm study dedicated transparent ruler vertically at the top of the color bar (0 level over the green top bar) and measure the length till the end of the red bottom bar

② Measuring the placement of the “X” of the color bar of the printed questionnaire:

- Place the study dedicated transparent ruler at the top of the color bar and measure the length till the intersection point level of the “X” marked on the color bar

③ Entering data in PIMS

- Enter the the length of the whole bar (in mm) and measured distance to the point level of “X” (in mm) in PIMS according to each taste assessment undergone by each participant.
- Data will be Entered by/Checked by two different Clinical Coordinators (Main & Back up) or designee.

Example: How to provide a mark (X) on the color bar.
